Item 13b: Any planned adjustment of the significance level due to interim analysis:

No adjustment of the significant level due to interim analysis are planned.

13c. Details of guidelines for stopping a trial early:

The following points are considered in planning the early stopping of the study:

1. That the intervention causes serious adverse effects in patients generating insecurity in its application.
2. That the investigators detect improbable, ineffective, or extreme differences between the CG and the IG.

3. New information emerges that raises serious safety issues or convincingly answers to the main question.

14. Timing of final analysis

Item 14: Timing of final analysis e.g all outcome analyzed collectively or timing stratified by planned length of follow-up

The follow-up will start in September 2020 until the established sample is met.

The last day of the study for each patient is going to be 40 days after hospital discharge.

Statistical analysis of clinical and biochemical variables will be performed on baseline, day three, hospital discharge and day 40. Analysis of overall survival and mortality will be performed from baseline to day 40 or patient death. Progression of patients to Mechanical Ventilation Assistance (MVA) will be performed from baseline until the last patient is intubated, mortality in patients with MVA will be performed from intubation to day 40 or death.

15. Timing of outcome assessments

Item 15: Time points at which the outcomes are measured

Survival and Mortality

- Overall survival and mortality: performed from baseline to day 40 or patient death.
- Progression of patients to Mechanical Ventilation Assistance (MVA): performed from baseline until the last patient is intubated.
- Mortality in patients with MVA: performed from intubation to day 40 or death.

Clinical and biochemical variables

- Delivered oxygen flow and maintenance of SpO₂ > 90%: will be analyzed at baseline and day three.
- qSOFA scale: will be analyzed at baseline compared with day three.

- Gastrointestinal function (average of gastrointestinal movements, abdominal distension, and Bristol scale): will be analyzed at baseline compared with day three.
- Laboratory parameters: will be analyzed at baseline, day three and hospital discharge.
- PHQ-9: will be analyzed at baseline and hospital discharge.

Follow-up at day 40

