- SpO2 without supplemental oxygen, use of home oxygen upon hospital discharge, days of supplemental oxygen use, post-covid syndrome, decrease in body weight: all will be analyzed from hospital discharge until day 40.

Section 4: Statistical Principles

16. Confidence intervals and p-values

Item 16: Level of statistical significance

P values ≤ 0.05 will be considered indicative of statistical significance in all cases. P values will be one-sided.

Item 17: Description of any planned adjustment for multiplicity, and if so, including how the type I error is to be controlled

This study will not analyze data that required multiplicity tests. To avoid type 1 error, an alpha value of 5% will be used (considering $p < 0.05$ significant), aberrant data will be eliminated, validated tests applicable to the study variables will be defined and established, specific inclusion criteria will be implemented for homogenization of the sample to avoid bias variables, and a specific sample size calculation will be performed.

Item 18: Confidence intervals (CI) to be reported

All the confidence intervals presented will be 95%.

19. Adherence and Protocol Deviations

Item 19a: Definition of adherence to the intervention and how this is assessed including extent of exposure.

The intervention will consist of: 1) 2 envelopes of NSS taken in a period of less than 15 minutes (without the presence of vomiting) after morning and afternoon meals during the first 21 days or until hospital discharge, 2) 1 capsule of *Saccharomyces Boulardii* before the NSS and 1 capsule with the second envelope for 6 days or until hospital discharge, 3) intramuscular B complex; 1 ampoule after meals for 5 days or at hospital discharge.

Adherence to treatment will be established as taking more than 95% of the NSS and not fasting for 2 consecutive days.

Item 19b: Description of how adherence to the intervention will be presented

The intervention will be applied by the research team, who will be responsible for the application and collection of data, which will be reported in daily formats in the morning and afternoon shifts.

The clinical investigators are going to prepare each supplement, administer, and witness each intake of the NSS, registering the time as well as any immediate side effects such as vomiting, bloating, and abdominal pain.

Item 19c: Definition of protocol deviation for the trial:

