Categorical data will be summarized by numbers and percentages. Normality tests will be applied to evaluate the distribution of the data. If the continuous data present a normal distribution, they will be assumed by mean, SD, and range. If they do not present a normal distribution, they will be summarized with the median and the IQR. Minimum and maximum values will also be presented for continuous data. Statistical significance tests will be performed between both groups in the baseline to rule out significant differences.

Section 6: Analysis

26. Outcomes definitions

Item 26a: Specification of outcomes and timings

Primary outcomes

- Overall mortality and survival will be assessed from the baseline to day 40.
- Progression to AVM will be assessed from baseline until the last patient is intubated.
- Mortality and survival in intubated patients will be assessed from baseline to day 40.

These results will be included in the results section of the manuscript.

Secondary Outcomes

Administration of supplemental oxygen flow, oxygen saturation (spO₂), qSOFA scale, and gastrointestinal function will be assessed by comparing at baseline to day 3 intragroup and intergroup. The PHQ-9 test will be assessed at baseline and at discharge between both groups.

These results will be included in the secondary outcomes section of the manuscript. Analysis of the association of baseline biochemical parameters and mortality will be considered in a table and in the secondary outcomes section of the manuscript.

The spO₂ without supplemental oxygen requirement, home supplemental oxygen requirement, post COVID syndrome, and body weight at day 40 will be analyzed between both groups in a table.

These results are included in the follow-up section of the manuscript.

Item 26b: Specific measurement and units

- SpO₂ (%)
- Mortality (days of death)
- Kilocalories (kcal / day)
- PHQ9 (pts).
- Temperature (°C).
- Hemoglobin (g / dL).
- Mean corpuscular volume (fL).
- Mean corpuscular hemoglobin concentration (g / dL).
- Leukocytes ($10^3 / \mu\text{L}$).
- Neutrophils (%).
- Platelets ($10^3 / \mu\text{L}$).
- Glucose (mg / dL).
- Total cholesterol (mg / dL).
- Triglycerides (mg / dL).
- Aspartate aminotransferase (U / L).
- Alanine aminotransferase (U / L).
- Albumin (g/dL).
- Blood Urea Nitrogen (mg / dL).
- Urea (mg / dL).
- Creatinine (mg / dL).
- Glomerular filtration rate
- Ferritin (ng / mL)
- Fibrinogen (mg / dL)
- C-reactive protein (mg / L)
- Dimer-D (ng / mL)

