- Procalcitonin (ng / mL)

27. Analysis methods

To consider statistical significance in the results, a value of $p < 0.05$ will be used.

The analysis of the primary and secondary outcomes is shown in the following table.

Variable	Outcome	Timing	Normality test	Summary results	Parametric test	Nonparametric test	Categorical data test	Analysis type
Overall survival	Primary	40 days follow-up	-	Kaplan-Meier	-	-	Log Rank	Intergruppal
Progression to intubation	Primary	until the last patient is intubated	-	Kaplan-Meier	-	-	Log Rank	Intergruppal
Survival in intubated	Primary	40 days follow-up	-	Kaplan-Meier	-	-	Log Rank	Intergruppal
Oxygen flow (L)	Secondary	Basal vs day 3	Shapiro-Wilk	Mean and SD	Paired T test	Wilcoxon	-	Intragruppal
qSOFA (pts)	Secondary	Basal vs day 3	Shapiro-Wilk	Mean and SD	Paired T test	Wilcoxon	-	Intragruppal
Defecations per day (No.)	Secondary	Day 3	Shapiro-Wilk	Mean and SD	Unpaired T test	Mann Whitney	-	Intergruppal
Distension (Yes/No)	Secondary	Day 3	Shapiro-Wilk	Proportions	-	-	Fisher	Intergruppal
PHQ-9 (pts)	Secondary	Basal vs Discharge	Shapiro-Wilk	Mean and SD	Paired T test	Wilcoxon	-	Intragruppal
Oxygen saturation >90%	Secondary	Day 3	Shapiro-Wilk	Proportion	-	-	Fisher	Intergruppal
Hydric balance	Secondary	Day 3	Shapiro-Wilk	Mean and SD	Unpaired T test	Mann Whitney	-	Intergruppal
Bristol scale "normal"	Secondary	Day 3	Shapiro-Wilk	Proportion	-	-	Fisher	Intergruppal
Saturation without supplemental O2	Secondary	Day 40	Shapiro-Wilk	Mean and SD	Unpaired T test	Mann Whitney	-	Intergruppal
Need for supplemental O2 at home	Secondary	Day 40	Shapiro-Wilk	Proportion	-	-	Fisher	Intergruppal
Days of supplemental O2 use at home	Secondary	Day 40	Shapiro-Wilk	Mean and SD	Unpaired T test	Mann Whitney	-	Intergruppal
Postcovid syndrome	Secondary	Day 40	Shapiro-Wilk	Proportion	-	-	Fisher	Intergruppal
Decrease in weight	Secondary	Day 40	Shapiro-Wilk	Proportion	-	-	Fisher	Intergruppal
Gastrointestinal symptoms	Secondary	Day 40	Shapiro-Wilk	Proportion	-	-	Fisher	Intergruppal

28. Missing data

Item 28: Missing data-reporting and assumptions/statistical methods to handle missing data

(multiple imputation)

Statistical methods to handle missing data will not be performed.

30. Harms

Item 30: Sufficient detail provided on summarizing harms

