Clinical Evolution	CG				IG				Intergroup p-value
	n	Baseline	Day 3	P value	n	Baseline	Day 3	P value	
Oxygen flow - L (intragroup)	40	5.9 ± 3.8	6 ± 4.4	0.919	40	6 ± 3.2	4.5 ± 3.5	0.014 *	
qSOFA - pts	40	0.42 ± 0.59	0.51 ± 0.57	0.608	40	0.65 ± 0.62	0.43 ± 0.49	0.040 *	
Number of defecations on day 3	37		0.81 ± 0.90		36		1.41 ± 1.13		0.014 *
Distension on day 3	31		51.60%		31		19.40%		0.008 *
PHO-9 test – pts (intragroup)	6	3.66 ± 2.5	1.50 ± 2.8	0.187	10	5.3 ± 3.4	1.9 ± 1.4	0.003 *	
Oxygen Saturation >90% on day 3 -%	40		85%		40		92.50%		0.241
Hydric Balance on day 3 - mL	17		123.4 ± 453.8		18		456.6 ± 485.5		0.043 *
Bristol scale on day 3 - %	24		33.30%		31		41.90%		0.356
40-day follow-up			Day 40				Day 40		
Saturation without Supplementary Oxygen - %	28		90.39 ± 3.4		38		92.08 ± 2.5		0.030 *
Need for home Oxygen flow - %	27		85.2%		39		66.70%		0.078
Time of home Oxygen use – days	17		57.6 ± 24.6		23		43.8 ± 16.2		0.098
Post-covid syndrome - %	24		37.50%		34		23.50%		0.195
Weight decrease - % of patients	11		72.70%		18		44.40%		0.135
Gastrointestinal symptoms - %	24		16.70%		37		8.10%		0.266

Table 2-A The following table shows the results of the intergroup analysis between the IG (Intervention Group) and the CG (Control Group) for different parameters in the baseline or with a complete 40-day follow-up. Deceased patients were excluded. * p-value <0.05.

Table 2-B. Association of baseline laboratory parameters and general mortality.

Baseline values	Discharge (n=72)		Death (n=8)		P value
	n	%	n	%	
Fibrinogen >700 mg/dL	13	18.50	6	75.00	0.002 *
Procalcitonin >0.5 ng/mL	4	5.5	4	50	0.003 *
Blood Urea Nitrogen >22 mg/dL	5	6.90	4	50	0.004 *
RCP >150 mg/L	28	38.8	7	87.5	0.011 *
Neutrophils >80%	45	62.50	8	100	0.031 *
Leucocytes >10 10 ³ /μL	18	25.00	5	62.50	0.040 *
Urea >40 mg/dL	12	16.6	4	50	0.047 *

Table 2-B. The results show the association between laboratory parameters taken in the baseline, with the overall mortality. Analysis was performed with Fisher's exact test. * p-value < 0.05.

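### Day-3 SpO2 is tested only as above or below 90%, which Items 15 and 26a do not describe alike; if NSS shifts the whole distribution the cut costs much of the power, so a baseline-adjusted full-scale analysis should be added

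*SAP*

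**What the plan says.** The only day-3 saturation analysis in the Item 27 table is a between-group Fisher test of a proportion: "Oxygen saturation >90% Secondary Day 3 Shapiro-Wilk Proportion - - Fisher Intergruppal". Three other parts of the SAP bear on this row.

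- Item 15 (timing of outcome assessments) uses the threshold: "Delivered oxygen flow and maintenance of SpO₂ > 90%: will be analyzed at baseline and day three".
- Item 26a (outcome definitions) does not: "oxygen saturation (spO₂), qSOFA scale, and gastrointestinal function will be assessed by comparing at baseline to day 3 intragroup and intergroup". Item 26b gives the unit of SpO2 as per cent.
- The day-40 row of Item 27 keeps saturation on its full scale: "Saturation without supplemental O2 Secondary Day 40 Shapiro-Wilk Mean and SD Unpaired T test Mann Whitney". That reading is taken off supplemental oxygen; the day-3 row carries no such condition.

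Table 1-A reports baseline SpO2 as mean and SD (CG 92.73 ± 4.17, IG 94 ± 3.18). Table 2-A reports the day-3 line, "Oxygen Saturation >90% on day 3", as 85% v 92.5% with 40 per arm and p=0.241. Item 16 sets the level and the direction: "P values ≤ 0.05 will be considered indicative of statistical significance in all cases" and "P values will be one-sided".

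**The concern.** SpO2 is recorded in per cent. Cutting it at 90% treats a patient at 91% the same as one at 98%. When most patients lie on one side of the cut, the test rests on very few of them: here 6 of 40 v 3 of 40 at or below 90%. A moderate general improvement in saturation could then pass unseen.

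At stake is part of secondary objective 2, the effect of NSS on clinical changes. A non-significant result from a weak test could be taken as showing that saturation did not improve. The items also leave open whether the day-3 outcome is the SpO2 value (Item 26a) or attainment of a target (Item 15), and only the second has an analysis.

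**Working it through.** **1. Reproduce the SAP's figure.** 85% and 92.5% of 40 are 34 and 37 patients. One-sided Fisher for 37/40 v 34/40 gives p=0.241, as tabulated; the two-sided value is 0.481.

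**2. What the test would need.** This step needs no distributional assumption. Hold CG at 34/40 and raise the IG count:

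| IG above 90% | One-sided Fisher p |
|---|---|
| 37/40 | 0.241 |
| 38/40 | 0.132 |
| 39/40 | 0.054 |
| 40/40 | 0.013 |

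At the reported control rate, only a perfect IG result reaches 0.05.

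**3. Power under a uniform shift.** Assume normal SpO2 with the same SD in both arms. The shift that turns 85% above the cut into 92.5% is d = z(0.925) − z(0.85) = 1.440 − 1.036 = 0.403 SD. With 40 per arm and one-sided 5%:

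- Fisher, by exact enumeration of both binomials: 16.7%.
- Unpaired t, noncentrality 0.403 × √(40/2) = 1.80 on 78 df: 55.7%.
- At two-sided 5% the figures are 10.0% and 42.9%.

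The effect here is back-calculated from observed rates, so this compares two tests on one scenario. It is not an estimate of the trial's true power. A simulation of whole-number SpO2 capped at 100 with a 0.4 SD shift gave Mann-Whitney 53%, t 54% and Fisher 18%, so rounding and the ceiling do not remove the difference.

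**4. Shifts on the percentage-point scale.** The pooled baseline SD is √((4.17² + 3.18²)/2) = 3.71. For control means from 92.73 to 94:

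| True shift | Fisher | t-test |
|---|---|---|
| 1.5 points | 24% to 16% | 56% |
| 2 points | 36% to 22% | 77% |

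**5. Using the day-40 means and SDs.** Take 90.39 ± 3.4 v 92.08 ± 2.5 as if they were day-3 values with 40 per arm. The normal model puts 54.6% v 79.7% above 90%. Power is 71% by Fisher and 81% by t. The loss is much smaller because the cut lies nearer the middle of the distribution.

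**6. Cases with little or no loss.**

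- Only the low tail differs, as might happen if oxygen flow is adjusted to hold saturation up. An illustrative simulation keeping 85% v 92.5% above the cut and the same distribution otherwise gave Fisher 16%, t 18% and Mann-Whitney 14%.
- The arm-specific baseline SDs are true SDs. Then 85% v 92.5% implies means of 90 + 1.036 × 4.17 = 94.32 and 90 + 1.440 × 3.18 = 94.58. The difference is 0.26 points, t power is 9%, and Fisher does better.

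**7. Why the full-scale analysis needs baseline adjustment.** IG starts 94 − 92.73 = 1.27 points higher, which is 1.27/3.71 = 0.34 SD and close to the 0.40 SD shift in step 3. Suppose there is no treatment effect and the baseline to day-3 correlation is r (an assumption; the documents give none). Given that gap, an unadjusted one-sided z-test rejects with probability 1 − Φ((1.645 − 0.342 × √20 × r)/√(1 − r²)). This is about 11% at r=0.3, 16% at r=0.5 and 21% at r=0.7, against a nominal 5%.

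**The case against.** The strongest reply is that the threshold is the outcome. Item 15 names maintenance above 90% and sets it beside delivered oxygen flow, and the Item 27 row carries that out. The 90% level also matches protocol section 8.4, where inclusion criterion 2 refers to saturation below 90%. A reader might infer that the cut is arbitrary or chosen after the fact; the SAP text does not support that. This part stands, and the >90% outcome should be kept.

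The second reply is that patients may be on oxygen at day 3. If flow is adjusted to hold saturation, improvement would appear as lower flow and mean SpO2 could stay flat. Table 2-A shows day-3 flow of 6 L in CG and 4.5 L in IG. The day-40 row, taken off oxygen, therefore shows that a full-scale analysis is feasible but is not a like-for-like precedent. This also stands, and it is why the size of the loss must be given as a range.

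The third reply is that this is one secondary outcome and the primary survival analysis does not depend on it. That is correct and limits the weight of the point.

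None of these replies explains why the recorded percentage should have no between-arm analysis at day 3 when Item 26a names it without a cut-off.

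**Conclusion.** The point holds in a conditional form. Item 27 analyses day-3 SpO2 only by the 90% cut, and Items 15 and 26a describe the outcome differently. Under a roughly uniform shift with a common SD, the cut loses much of the power: about 17% v 56% at the SAP's own day-3 rates, and 71% v 81% with the day-40 figures. If only the low tail differs, or the arm SDs truly differ as at baseline, there is little or nothing to gain. No day-3 mean or SD is given, so the documents do not settle which case applies.

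Two stronger readings are tempting. One is that most of the power is lost as a matter of fact; that follows from the shift model and the control rate near 85%, and the other cases above contradict it as a general statement. The other is that a real saturation benefit was missed; the documents contain no day-3 values that could show this. What can be said is that p=0.241, from 6 v 3 patients, is not evidence that NSS has no effect on saturation.

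**What to change.** - Reconcile Items 15, 26a and 27, so that the SAP states whether day-3 saturation means the SpO2 value, attainment of >90%, or both.
- Add to Item 27 and Table 2-A a between-arm analysis of day-3 SpO2 (%) on its full scale, adjusted for baseline SpO2: ANCOVA, or a rank-based version if the data are skewed. Report the adjusted difference with a 95% CI and interpret it beside day-3 oxygen flow.
- Keep the proportion above 90% as the Item 15 responder summary, and state that its p-value does not show absence of effect.
- Label the added analysis as specified after results were known.

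The cost is some SAP wording and one extra analysis of data already recorded, with no new patients or measurements. The downside is one more secondary analysis, and it can only be exploratory.

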2. To evaluate the effect of NSS on clinical and biochemical changes among patients.
3. To evaluate the effect of NSS on the biochemical status associated with overall mortality.

Study hypotheses

The null hypothesis: The nutritional support system will not reduce mortality or increase survival in patients with COVID-19 in stage III and comorbidities compared to conventional nutritional therapy.

Research hypothesis: The nutritional support system will reduce mortality and increase survival in patients with COVID-19 in stage III and comorbidities compared to conventional nutritional treatment.

Section 3: Trial Methods

9. Trial design - description of trial design

Item 9: Brief description of trial design including type of trial

Randomized, blinded, controlled clinical trial. Selected patients will be randomized into two groups: 1) Control Group (CG) will receive the hospital diet and 2) Intervention Group (IG) will receive the hospital diet and the NSS. Treatment allocation will have a 1:1 ratio.

10. Randomization

Randomization will be performed using a raffle; eighty numbers are to be placed (from 1 to 80). Subsequently, each number will be randomly selected from the raffle and sequentially assigned to one of the two groups, until reaching 40 numbers per group. Each number represents the moment the patient enrolls. In this way, once the recruitment starts, the first patient will be assigned number one; the second will be number two, and so on.

11. Sample size

Item 11: Full details of the same size calculation or alternatively reference to sample size calculation in protocol (instead of replication in SAP).

The sample size will be calculated using the formula: $n = \frac{z^2 p q}{e^2}$, where: 95% confidence level ($z = 1.96$), $p = 0.975$, $q = 0.025$, with a margin of error of 5% ($e = 0.05$), obtaining 38 patients per group for the sample.

12. Framework

Item 12: Superiority, equivalence or non-inferiority trial hypothesis testing framework, and wick comparisons will be presented on this basis.

The effect of NSS in increasing survival and reducing mortality in patients with COVID-19 will be demonstrated by the significant superiority of IG over CG.

13. Statistical Interim analyses and stopping guidance

Item 13a: Information on interim analyses specifying what interim analyses will be carried out and listing of time points:

No interim analyses are planned in the study.

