- Not meeting inclusion criteria including patients with respiratory rate disturbance (>30 bpm), glycemia >250 mg/dl, Glomerular filtration rate (GFR) < 60 ml/kg/m², platelets level (<150 10³ /L), concomitant autoimmune diseases (hypothyroidism, rheumatoid arthritis, atopic dermatitis), and/or respiratory disorders (bronchial asthma, obstructive sleep apnea syndrome, chronic lung lesions).
- Declined to participate.
- Randomization of all patients.
- Assignment of 40 patients to CG (received hospital diet and hospital treatment) and 40 patients to IG (received intervention - NSS, probiotics, B complex, hospital diet, and hospital treatment).

- Report of incidents.
- Variables analyzed in both groups with their evaluation periods.
- Primary outcomes.

24. Withdrawal/ Follow-up - level of withdrawal

Item 24a: Level of withdrawal e.g. from intervention and/or from follow up

The withdrawal levels that could be present in the study are listed as follows:

1. Participants can withdraw from the intervention and follow-up stops but the information collected is considered as data.
2. If patients decide to withdraw from follow-up, they are asked to allow us to use the data collected to date.
3. If a patient does not allow his/her data to be analyzed, they will not be considered in the analysis.
4. If the patient presents secondary reactions or does not adequately follow the treatment, they should leave the study and their data will be considered for the analysis.
5. Data from patients who die will be considered in the analysis.

Item 24b: Timing of withdrawal/lost to follow up data

The report of withdrawals and losses will be established in the CONSORT diagram, Kaplan-Meier curves, and primary outcomes section, where the timing of withdrawals will be mentioned, as well as the analysis and number of deaths.

Item 24c: Reasons and details of how withdrawal/lost to follow up data will be presented

Reasons for patients deciding to withdraw and deaths from COVID-19 complications will be presented on the CONSORT diagram, Kaplan-Meier curves, and in the primary outcomes section.

25. Baseline patient characteristics

Item 25a: List of baseline characteristics to be summarized

The clinical characteristics, demographic analysis and baseline values will be presented in tables. Details of the randomization will be mentioned in the methods section.

Item 25b: Details of how baseline characteristics will be descriptively summarized

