D dimer – ng/mL	291.2 ± 179.9	444.9 ± 954.9	0.927
Creatinine – mg/dL	0.88 ± 0.31	0.86 ± 0.22	0.734
Urea – mg/dL	33.95 ± 15.84	32.95 ± 10.78	0.710
BUN – mg/dL	15.87 ± 7.39	15.43 ± 5.02	0.690
GFR – mL/min/1.73 m ²	90.15 ± 20.2	93.59 ± 17.4	0.673
Procalcitonin – ng/mL	0.364 ± 0.6	0.18 ± 0.188	0.356

The comparison of both groups in the baseline did not show a significant difference in any item analyzed in this study.

SD, Standard Deviation. CG, control group. IG, intervention group. MNA, Mini Nutritional Assessment.

Figure 2. Kaplan-Meier general survival curve from CG and IG patients

[figure not shown]

Figure 2. Kaplan-Meier general survival curve from CG and IG patients.

The proportion of patients in the IG (blue line) and the CG (red line) included in the study and completed a 40-day follow-up from September 2020 to April 2021. The cumulative proportion of surviving patients was estimated with the Kaplan-Meier method and compared in both groups, from the CG died seven of 40 patients (surveillance 82.5%, mean 36.22, 95% of confidence interval [CI] 33.46 to 38.98), otherwise from de IG died one of 40 patients (surveillance 97.5%, mean 39.31%, 95% of [CI], 37.98 to 40.64). This showed a significant difference of IG compared to CG * $p=0.027$ (Log Rank test, 95% of [CI]).

Figure 3. Kaplan-Meier survival curve from patients Receiving Mechanical Ventilation of the CG and IG.

Figure 3-A

[figure not shown]

Figure 3-B

[figure not shown]

Figure 3. Kaplan-Meier survival curve from patients Receiving Mechanical Ventilation of the CG and IG.

The proportion of patients with MVA from CG and the IG were included in the study and completed 40-day follow-up from September 2020 to April 2021. **(Figure 3-A)** IG and CG were analyzed with the Kaplan-Meier method comparing both groups to MVA progression, from CG seven patients progressed to MVA (17.5%, mean 9.68%, [IC] of 95%, 8.66 to 9.80); meanwhile, from IG three patients progressed to MVA (7.5%, mean 9.68%, [IC] of 95%, 9.34 to 10.03), this represents a 10% decrease in MVA progression of IG in comparison with CG. **(Figure 3-B)** In overall survival and mortality with MVA, five out of seven patients died in CG (71.4%, mean 19.42, [CI] of 95%, 13.09 to 25.76). One out of three patients died in IG (33.5%, mean 26.66, [IC] of 95% 11.73 to 41.6), this represents the 38.1% decrease in mortality with MVA in IG compared to CG.

Table 2-A. Clinical evolution and 40-day follow up.

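### Day-40 secondary outcomes are analysed only in survivors with data, with no missing-data method; more control than intervention patients are missing, and the results shift either way with what is assumed about them

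*SAP*

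**What the plan says.** SAP Item 28 disposes of missing data in one sentence: "Statistical methods to handle missing data will not be performed". Item 27 assigns t or Mann-Whitney tests and Fisher tests to the day-40 outcomes and gives no rule for patients who die or have no measurement. Item 20 describes the patients and the two groups but names no analysis set (intention-to-treat, complete-case or survivors).

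Two passages deal with deaths. Item 24a, point 5, in the list of withdrawal levels, says: "Data from patients who die will be considered in the analysis". The legend of Table 2-A, which holds the day-40 results, says: "Deceased patients were excluded".

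Item 9 sets the allocation: "Treatment allocation will have a 1:1 ratio". The Figure 2 legend gives the deaths: "from the CG died seven of 40 patients" and "from de IG died one of 40 patients". Item 16 makes p-values one-sided, with significance at 0.05.

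**The concern.** Using only patients with a recorded value is valid if, within each arm, whether a value is missing has nothing to do with what it would have been. The SAP neither states nor tests that assumption. It matters most when the arms lose different numbers of patients, and Table 2-A shows that they do.

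Two things shrink the day-40 groups. Deaths remove seven CG patients and one IG patient; this is truncation by death rather than missing data. Survivors without a measurement then drop out as well, mostly from CG. What remains is no longer the randomised comparison. At stake are the one starred day-40 result (saturation, p=0.030) and the reading of the non-significant rows.

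**Working it through.** **Inputs.** 40 randomised per arm (SAP Items 20 and 23). Deaths are 7 CG and 1 IG (Figure 2 legend), so survivors are 40 − 7 = 33 and 40 − 1 = 39, total 72, which agrees with the 72 discharged in Table 2-B. Observed n, percentages, means and SDs are from Table 2-A.

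**Reproducing the SAP's figures.** Event counts are percentage × n. For home-oxygen need, 0.852 × 27 = 23 and 0.667 × 39 = 26. One-sided Fisher tests on observed patients give:

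- home oxygen, 23/27 v 26/39: 0.078
- post-COVID syndrome, 9/24 v 8/34: 0.195
- weight decrease, 8/11 v 8/18: 0.135
- gastrointestinal symptoms, 4/24 v 3/37: 0.266

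All four match the table, so these rows are complete-case and one-sided. For saturation (90.39 ± 3.4, n=28 v 92.08 ± 2.5, n=38), a two-sided Welch t-test gives 0.031 against the reported 0.030. The test used may have been Mann-Whitney, which summaries cannot reproduce.

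**Missing among survivors** (survivors − n observed, two-sided Fisher):

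| Outcome | CG of 33 | IG of 39 | p |
|---|---|---|---|
| Home-oxygen need | 33 − 27 = 6 (18%) | 39 − 39 = 0 | 0.007 |
| Gastrointestinal symptoms | 33 − 24 = 9 (27%) | 39 − 37 = 2 (5%) | 0.018 |
| Saturation | 33 − 28 = 5 (15%) | 39 − 38 = 1 (3%) | 0.087 |
| Post-COVID syndrome | 33 − 24 = 9 (27%) | 39 − 34 = 5 (13%) | 0.145 |
| Weight decrease | 33 − 11 = 22 (67%) | 39 − 18 = 21 (54%) | 0.34 |

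**Bounds for home-oxygen need.** IG is complete at 26/39 = 66.7%. The reported difference is 85.2 − 66.7 = 18.5 points.

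- None of the six missing CG survivors needed oxygen: 23/33 = 69.7%, difference 3.0 points, one-sided p=0.49 (two-sided 0.81).
- All six did: 29/33 = 87.9%, difference 21.2 points, one-sided p=0.032 (two-sided 0.051).

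**Bounds for two other binary rows** (one-sided p). The first figure assumes that no missing CG patient and every missing IG patient has the event; the second assumes the reverse.

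- Post-COVID syndrome: 27.3% v 33.3% (p=0.79) to 54.5% v 20.5% (p=0.003).
- Gastrointestinal symptoms: 12.1% v 12.8% (p=0.67) to 39.4% v 7.7% (p=0.001).

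**Tipping point for saturation.** Let the five missing CG survivors have mean μ and SD 3.4 (an assumption). The CG mean becomes M = (28 × 90.39 + 5μ)/33, and its variance becomes [27 × 3.4² + 4 × 3.4² + 28(90.39 − M)² + 5(μ − M)²]/32. IG stays at its 38 observed patients; its one missing survivor is left out.

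| μ (%) | M | Difference IG − CG | Welch p, two-sided |
|---|---|---|---|
| 88 | 90.03 | 2.05 | 0.006 |
| 89 | 90.18 | 1.90 | 0.010 |
| 90.39 (observed CG mean) | 90.39 | 1.69 | 0.02 |
| 92.08 (observed IG mean) | 90.65 | 1.43 | 0.05 |
| 93 | 90.79 | 1.30 | 0.08 |
| 94 | 90.94 | 1.14 | 0.13 |

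Halving for a one-sided test gives about 0.025 at the IG mean, 0.04 at 93% and 0.066 at 94%.

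**Counting deaths.** Alive without home oxygen is 39 − 26 = 13 of 40 in IG. In CG it is 27 − 23 = 4 known, plus 0 to 6 of unknown status, so 4/40 to 10/40. Two-sided p runs from 0.027 to 0.62 (one-sided 0.013 to 0.31).

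**The case against.** The strongest reply is that only secondary outcomes are involved. The Kaplan-Meier analysis counts all eight deaths, and a patient who has died has no day-40 saturation to analyse. All of that stands.

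A reader might infer that the Table 2-A legend flatly contradicts Item 24a(5). The documents do not support this. Point 5 names no outcome, and the survival curves and Table 2-B already satisfy it. It is an ambiguity to settle outcome by outcome. The legend is itself loose: several day-3 rows in the same table show 40 patients per arm, so the exclusion cannot apply to them.

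A reader might also infer that loss differs by arm beyond chance throughout. It does so for two of the five rows tested, home-oxygen need and gastrointestinal symptoms. It does not for saturation (p=0.087), post-COVID syndrome (p=0.145) or weight (p=0.34), where most values are missing in both arms.

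Finally, scoring deaths as the worst outcome would change the question and bring the primary mortality result into secondary outcomes. Item 24a(5) prescribes no such scoring, and adopting it now would follow sight of the 7 v 1 deaths. That counts against making it the main analysis; it does not count against a labelled sensitivity analysis.

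**Conclusion.** The concern holds for the day-40 secondary outcomes. Item 28 leaves them resting on an untested assumption, and the SAP's own denominators show more missing CG than IG survivors in each row tested, clearly so in two. On the SAP's one-sided rule, the home-oxygen result can fall on either side of 0.05 depending on six CG survivors. The saturation result strengthens if the five missing CG survivors did worse than those observed and weakens if they did better. Two-sided, it is borderline when their mean equals the IG mean; one-sided, it is lost only somewhere between 93% and 94%.

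A reader might infer that the day-40 findings are biased in favour of the intervention, or cannot be trusted at all. Neither is shown. Excluding deaths removes the worst outcomes mainly from CG and could hide benefit, while plausible values for missing survivors could reduce or remove it. Sensitive to missing data is the accurate description.

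The saturation figures rest on summary statistics, an assumed SD of 3.4 in the missing patients and a t-test in place of a possible Mann-Whitney test. The binary bounds need only the tabulated counts.

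**What to change.** Replace the Item 28 sentence with a rule covering each day-40 outcome:

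- State how deaths are handled for that outcome, and reconcile Item 24a(5) with the Table 2-A legend. Limit the legend to the rows where it applies.
- Report n observed, n alive and n randomised by arm.
- For binary outcomes, give best- and worst-case bounds for missing survivors, with the sidedness of each p-value stated.
- For saturation, give a tipping-point analysis that runs both above and below the observed CG mean, using patient-level data and the test actually applied.
- Optionally add alive without home oxygen as a sensitivity analysis, with bounds for the six CG patients of unknown status (IG 13/40 v CG 4/40 to 10/40).

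Because the results are already in the SAP, label all of these as post hoc sensitivity analyses, and describe the day-40 findings as sensitive to missing data.

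The cost is some SAP wording and a few analyses on existing data. No patient procedure changes. The downside is that some results will look less certain.
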